# 3. Y-Check Programme

The Y-Check programme comprises of health and well-being education classes in schools and check-up visits at two time points during the adolescent period (early and middle/late adolescence) delivered at both school and community venues. In addition, the programme will include community mobilisation, and school and health facility staff training and orientation. The programme will be co-created with adolescents, their caregivers, policy-makers, teachers, and healthcare providers, ensuring that it aligns with national priorities, and is accessible and acceptable to users.

#### 3.1 Target conditions and behaviours

Informed by a scoping literature review and expert consultation during the 2019/20 formative work, conditions and behaviours were selected based on their prevalence, and the ability to diagnose and treat. The conditions and behaviours to be screened for and the rationale for their choice is summarised in **Table 1**. The target health conditions and behaviours will be finalised towards the end of Phase 1 following additional stakeholder engagement and pre-testing of screening tools and referral pathways (see section 5.1).

Table 1: Rationale for choice of conditions and behaviours included in checkup visit.

	Rationale				
Psychosocial issues	The quality of an adolescent's home and working/school life, and their				
(difficult home	relationship with their peers can impact on their mental health.				
environment, challenges	Identifying and helping adolescents who are living in difficult situations				
with education or	will improve their health and well-being.				
employment, participation					
in social activities, and					
safety and security)					
Drug, alcohol and tobacco	Risk behaviours often start in adolescence and contribute to morbidity				
use	and mortality in adolescence as well as increasing later risk of NCDs				
Mental Health	Identified as a leading cause of morbidity among adolescents and is				
	associated with suicide and increased risk behaviours.				
Growth, nutrition, and	Poor nutrition in adolescence can affect health and well-being, adult				
physical activity	body size, and may also affect the nutritional status of children born to				
	women who were malnourished in adolescence.				
	Obesity and lack of exercise in adolescence are risk factors for NCDs in				
	adulthood.				
Anaemia	Anaemia is a leading cause of morbidity among adolescents.				
Oral health	Untreated dental cavities can cause severe pain, infection, and problems				
	with eating, speaking, and learning in children and adolescents. 				
	Risk reduction counselling is insufficient without the availability of				
SRH & HIV prevention	HIV prevention commodities.				
	Provision of MHM and other SRH products enhances acceptability by				
	community and adolescents.				

	Testing for STI's important as syndromic management not very effective.					
Immunisation	Completing immunisation schedules will protect adolescents against preventable diseases in addition to contributing towards the development of herd immunity in the community.					
Eyesight	Untreated eyesight problems can impact on educational attainment, and physical and mental health.					
Hearing	Untreated hearing problems can impact on educational attainment, and physical and mental health.					
Physical impairment	Untreated physical impairment can impact on an adolescent's ability to perform everyday tasks, and impact on their educational and work prospects.					
Epilepsy	Epilepsy is one of the most common neurological conditions which carries a high burden of disease when left untreated. A large treatment gap exists in LMICs. 					
Blood pressure (Y-Check	Prehypertension and hypertension in adolescence are predictors for					
2)	developing manifest hypertension as adults. 					
Schistosomiasis	In the short term, schistosomiasis during adolescence can cause anaemia, stunting and a reduced ability to learn (WHO). In the long-term it can cause considerable disability and reduce the individual's work productivity and even death (WHO).					

# 3.2 Setting

Chitungwiza is the third largest city in Zimbabwe, located approximately 25km south of the capital city, Harare, and has a population of about 456 000. The houses are mostly high-density, single story, detached units with small yards that are generally used for growing vegetables. Most of the people work in Harare, as there is little industry in Chitungwiza. There is one tertiary hospital, 4 public primary healthcare facilities, 20 private medical facilities, and 34 government primary schools (all mixed sex).

Four communities and four schools were chosen by Chitungwiza stakeholders to take part in Y-Check formative work in 2019/20 (High schools: Seke High 6, Zengeza High 1; Primary schools: Dungwiza Primary, Chinembiri Primary). Communities and schools were selected to represent the diversity of wards in the town and taking into account the economic disparities. The selection of the schools and communities for this study will be conducted in collaboration with stakeholders including MoPSE, MoHCC, and the study Youth Advisory Group (YAG) taking into consideration previous participation in the formative work and the location of other ongoing projects. We will aim to work in four distinct communities which are representative of the urban, peri-urban and rural populations of Chitungwiza. Potentially eligible schools must meet the following criteria:

- Student population of at least 200 learners in Grade 5, 6, or 7 (Y-Check 1 target intervention year) or at least 75 learners in Form 3, 4 or 5 (Y-Check 2 target intervention year).
- Located in or close to one of the selected study communities

# 3.3 Community engagement

This study will build on the community engagement established during the 2019/20 formative work. Briefly, this comprised a detailed stakeholder analysis (meetings and discussions with stakeholders including health services, CBOs, non-governmental organisations (NGOs)), and interviews and discussions with youth, family members and other community gatekeepers. Workshops were held with youth selected from study communities to inform the design, content and delivery of the intervention and to ensure they are equitable partners in the research process.

In Year 1 a **Community Steering Committee** (**CSC**) comprising key community leaders and stakeholders will be set up to facilitate input from, and feedback to, participating communities. Strong community engagement will allow the establishment of a partnership between communities, participants and researchers to ensure the latter discharge their responsibilities ethically in the study communities. A **Youth Advisory Group** (**YAG**) will provide a forum for adolescents to input into the programme. The YAG will meet with research staff a minimum of 4 times a year, be active participants in programme design and dissemination workshops, and help to ensure that the programme meets the needs of adolescents. Community engagement will be an ongoing process through regular contacts with stakeholders and the YAG.

In addition, a key aspect of building confidence within communities is the knowledge that the study has the support and partnership of the government. Partnership with the MoHCC and MoPSE was sought at the inception of the study and input on this protocol was provided by [name] and [name] (MoHCC) and [name] and [name] (MoPSE). Support and permission to conduct the study will be sought from the Harare Provincial Medical Directorate, Chitungwiza City Health Director, Local Authorities, and Health Services Director. At community level, permission will be sought from the Provincial and District Administrators for the use of community centres.

# 3.4 School orientation and training

Study schools will be contacted the term before the team are due to arrive in the school. The study team will agree with the school principals on the most appropriate days, times, and location for the service delivery. They will also agree on the best timing for the delivery of whole-class education sessions in line with the School Health Policy. School staff will receive information on the programme including an overview of adolescent health and well-being, the conditions to be screened for and the referral pathways available.

#### 3.5 Health service provider orientation and training

The local health services (e.g. the primary health care clinics) are the custodian of health of the community and collaboration with them is essential for ensuring both care of Y-Check clients beyond the intervention and to facilitate scalability. The intervention team will work with the nurses at the clinics to ensure that HIV and other services provided by Y-Check are integrated with routine services e.g. ensuring that all youth diagnosed with HIV through Y-Check are registered into the National antiretroviral therapy (ART) programme. Regular meetings will be held between the intervention team and health service staff to ensure that strong relations are maintained.

Social service, food supplementation and CBOs/NGOs providing specialist services will also be engaged. The Y-Check programme staff will hold detailed discussions with potential referral services and review the appropriateness and quality of services that they are able to offer, and where necessary to agree a fee for services provided. Additional training and support will be provided to referral services to support their provision of youth-friendly health services. Service providers who are likely to receive

referrals from Y-Check will be orientated on the use of referral vouchers. Adolescents will be given referral vouchers during the check-up visit so that they do not need to pay for the referral. The Y-Check team will then reimburse the service provider for any vouchers that are redeemed. The referral protocols will be co-designed with service providers during Phase 1 including pre-testing and piloting.

#### 3.6 Whole school sessions

Whole-class education sessions will be delivered in line with the School Health Policy on nutrition, exercise and oral health; mental health, and alcohol, tobacco, and drug use, puberty, menstrual health, sexual health, and early marriage. The content will be age appropriate and may vary between Y-Check 1 (primary schools) and Y-Check 2 (secondary schools).

# 3.7 Check-up visits

The target school grades and age-ranges will be agreed in consultation with MoPSE, MoHCC and other stakeholders during Phase 1 of the study and will align with existing or planned school services. The timing of the check-up visit will be agreed with teaching staff, students, and community stakeholders. Y-Check will target two age cohorts, Y-Check 1 (10-14 year olds) and Y-Check 2 (15-19 year olds).

#### Y-Check 1

The first visit, Y-Check 1, will target the 10-14 year old age cohort and will be delivered exclusively in primary schools as a very high proportion of the target population are attending primary schools (90.5% (MICS 2019). The intervention is likely to target adolescents in Grade 5 where the majority of students are aged 10 years (45% aged 10 years in MICS 2019) or 11 years (21% aged 11 years in MICS 2019). However, as a result of starting school late or repeating years there are a proportion of students who are over age for their grade (10% were aged 12 and 4% were aged 13 years).

#### Y-Check 2

The second check-up visit, Y-Check 2, will target the 15-19 year old age cohort and will take place both in secondary schools and at community venues (16-19 years only in the community). In schools, Y-Check 2 is likely to target adolescents in Form 3 where most learners are aged 15 or 16. School attendance drops off in secondary schools and an estimated 50% of 16 and 17 year olds are out of school. We are therefore proposing to also deliver Y-Check 2 at community venues to adolescents aged 16-17 years who are not attending school. Community venues will be multi-purpose use locations, such as a community centre. Using methods developed to deliver sexual and reproductive health services in the ongoing CHIEDZA trial (www.chiedza.co.zw) we will create bespoke 'hubs' in existing community centres to deliver Y-Check 2. This will be accompanied by mobile outreach at locations frequented by adolescents (e.g. shopping centres, workplaces, bars, sports venues) to advertise the check-up visits and achieve high coverage.

Information about Y-Check services will be shared with parents/guardians and community members before the intervention team visit the school/community venue. Consent procedures will differ for those recruited in schools (Y-Check 1 and Y-Check 2) and those recruited in the community.

• School recruitment (Y-Check 1 (10-14y) & Y-Check 2 (15-19y)): All students in the Y-Check target classes/forms will be eligible to participate if their parent/guardian has signed a consent form and the student has provided written assent.

• Community recruitment (Y-Check 2 (16-19y)): Participants receiving Y-Check 2 services in the community will provide their own verbal consent. Parent/guardian consent will not be required for adolescents receiving services in the community, but participants will be encouraged to share information and results with their parents/guardians or another trusted adult.

Parents/guardians/students can choose to participate in the full screening visit or part of the screening visit e.g. the pre-consultation questionnaire and nurse review only.

#### 3.7.1 Information, education and communication (IEC)

During check-up visits in all settings, IEC materials about mental health, diet and exercise, oral health, drugs and alcohol, sexual and reproductive health (SRH), HIV, safety, and general health will be available in the form of video clips, games, information leaflets and social media postings. IEC materials will be appropriate for various age and literacy levels. Materials will also be provided to help adolescents to navigate the health system and find a trusted provider if they have an urgent issue. The Y-Check team will provide details on how clients can get tailored advice or further information from the Y-Check team following the check-up visit, for example, if they can't access the trusted provider. The format of this support will be designed with young people during Phase 1 and may take the form of a live chat option on a Y-Check webpage, a phone number that can be messaged (via SMS or WhatsApp), or a hotline phone number that can be called free of charge. All IEC materials to be shared in schools will be submitted to the Curriculum Development and Technical Services Department for confirmation of curriculum alignment.

#### 3.7.2 Screening tests and treatment/referral protocols

Screening tests and detailed treatment/referral protocols will be developed and implemented in line with national guidelines and best practice. As the screening of adolescents in Zimbabwe for many of the conditions listed below has not been implemented before, identifying locally accessible care pathways will involve working with existing services and potentially developing novel opportunities and pathways to address current gaps in service provision. During Phase 1 we will form a working group comprised of study investigators, health and social care, and disability stakeholders to decide on the final screening and referral strategies. Draft protocols are described here and in **Appendix 1**.

Psychosocial issues and alcohol, tobacco and substance use

Participants will respond to questions about their home, school/work, social activities, and exposure to violence and other risky situations using questions adapted from multi-domain psychosocial screening tools such as HEEADDSSS (Home, Education and Employment, Eating, peer activities, Drugs, Sexuality, Suicide/Depression, Safety and Security, Screens and Strengths) and other validated substance abuse questionnaires such as CRAFFT and Alcohol, Smoking and Substance Involvement Screening Test - Youth (ASSIST-Y)

Adolescents who are identified as high-risk including those who report experiencing or perpetrating violence, addiction to drugs or alcohol, or being suicidal will be referred to health, social and/or police services. The Y-Check team have a legal obligation to report certain findings such as domestic violence/abuse of children (<18 years of age) to the relevant authorities (e.g. the relevant department of the police, and the social welfare department for domestic violence or abuse). Decisions around referral will take place in consultation with school staff, parents/guardians and/or trusted adults who have been nominated by older adolescents (see section 7.6).

#### Mental Health

Mental health will be measured in a stepped screening process using validated tools for depression and anxiety e.g. the Shona Symptom Questionnaire (SSQ), Patients' Health Questionnaire – Adolescent (PHQ-A), Generalised Anxiety Disorder (GAD-7), Pediatric Symptom Checklist (PSC-Y),or Hospital Anxiety and Depression Scale (HADS).  Those with a score indicating risk of common mental disorders (CMD) will be referred to the nurse or counsellor for additional assessment and counselling. The nurse will then refer those with moderate anxiety or depression to the Friendship Bench for Youth (YouthFB) intervention or other youth-friendly counselling services. Participants who indicate severe mental health disorders that require more urgent care will be referred immediately as a 'red flag' case to the nearest health facility or youth-friendly counselling services.

#### Growth and nutrition

Participants will report on their diet and exercise in the pre-consultation questionnaire. All participants will have their waist circumference, mid-arm circumference (MUAC), Body Mass Index (BMI), and Body Volume Index(BVI) or Bioelectrical impedance analysis (BIA) measured to assess nutritional status. MUAC measurements will be compared to age and gender specific standards. Adolescents who are overweight or obese will receive counselling and information on diet and exercise. Adolescents who are severely underweight will be referred to food supplementation services.

All participants will be screened for anaemia by taking a finger-prick sample of blood which will be tested during the check-up visit using HemoCue. If anaemic (children <11 years Hgb <11.5g/dL, 12-14 years <12g/dl, females >15 years <12g/dl, males > 15 years <13 g/dL): Iron and folic acid-supplementation (3 months supply) will be provided. If severely anaemic (<8g/dl) the participant will be referred to health facility for investigation.

#### Oral health

Participants' teeth will be visually inspected to identify dental caries, pits or fissures in the enamel, abscesses, swelling or oral lesions. Untreated caries, pits or fissures will have an application of silver diamine fluoride (SDF). If the adolescent has also reported pain or swelling they would also be referred to a dentist. For all participants, a fluoride varnish will be applied to all their teeth (irrespective of condition). A gift of a tube of toothpaste and a toothbrush with be provided to allow participants to practice the oral health guidance that they will have received from the research team. A demonstration of how to brush teeth correctly will be included in the IEC materials (see section 3.6.1).

#### Voluntary male circumcision (VMMC) (Y-Check 2 in the community hubs only)

During the background assessment males accessing services in the community will be asked if they are circumcised. If necessary, they will also undergo a visual inspection, respecting their privacy. Privacy will be respected during any visual inspection by the inspection happening in a closed room or tent where only the participant and the health worker are present. If they are not circumcised and request VMMC then expedited referral will be arranged.

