#### **Schistosomiasis**

A national study of schistosomiasis in Zimbabwe published in 2014 showed a prevalence of 5.2%

(95%CI 2.9,8.6%) for the combination of S. haematobium and S. mansoni in primary schools in Chitungwiza and of 9.6% (95%CI 8.0,11.5%) in Harare (Midzi et al., 2014). In Chitungwiza, the estimated prevalence of S. haematobium was almost 10 times higher than that of S. mansoni. We will therefore test initially only for S. haematobium using a urine filtration lab test to detect the parasites in the urine. Considered the 'gold' standard, this test shows high sensitivity and specificity. We will review the screening procedure after the first 200 adolescents have been screened. If the prevalence of S. haematobium is 15% or higher (n=200 will allow 5% margin of error on prevalence estimate) then we will additionally test urine samples for S. mansoni using the commercially available urine-based Point of Care test, based on detection of circulating cathodic antigen (CCA). In this situation, the initial 200 adolescents will be revisited so that they can also be tested for S. mansoni. Detection of schistosomiasis will require collecting urine specimens which will be tested in the lab or on-site as stated above. National protocols for treatment will be provided as needed for those who test positive."

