# 6. Statistical considerations and Data analysis

## **6.1 Outcomes**

Outcomes (see Section 4.3.2) will be assessed using:

- Programme data collected during the check-up visit and at the referral services
- Research data collected through the pre-consultation questionnaire, exit interview, and during follow-up visits in the subsequent 12 months.
- School register data for the 12 months before and after Y-Check school visits

The primary outcome will be the proportion of those screening positive for at least one condition who receive appropriate on-the-spot care or complete appropriate referral for all identified conditions within 4 months.

- Completed referral is defined as attending at least the first referral appointment. We expect referral/treatment to have occurred within 4 months.
- Where a client has been diagnosed with more than one condition they must have had completed
  care or referral for each of those conditions in order to be included in the numerator for the
  primary outcome.

Secondary implementation outcomes:

- The proportion of those who screen positive for individual conditions that have had their condition correctly managed within 4 months
- Yield of previously undiagnosed and un-referred conditions
- Intervention acceptability, adoption, appropriateness, feasibility, fidelity and cost (see Process Evaluation Section 4.3.3 for further details)

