# **Appendix 1: Conditions with correct management and subsequent outcomes**

Condition/risk behaviour	Screening tool	Primary Outcome: Appropriate on the spot care or complete appropriate referral		Secondary clinical or behavioural outcomes
		Appropriate on the spot care	Complete appropriate referral	
Psychosocial issues (home environment, education/employment, violence etc.)	Questions from HEEADSSS 	Counselling +/- referral	Attend first meeting with social services	Severity of psychosocial issue
Alcohol, tobacco and substance use	ASSIST-Y 	Brief intervention +/- referral	Attend first meeting with counsellor	Alcohol use Tobacco use Substance use
Common mental health disorders	Shona symptom questionnaire (SSQ) 	Counselling +/- referral to Youth Friendship Bench if SSQ score >=8. If 'red flag' refer to nearest health facility.	Attend first meeting of Youth Friendship Bench	Severity of symptoms
Low levels of physical activity	Questions from HEEADSSS 	Counselling and advice		Level of physical activity
Poor diet	Questions from HEEADSSS 	Counselling and advice +/- referral	Attended first appointment at food supplementation services	Frequency of fruit and vegetable intake Frequency of sugary beverage intake
Underweight	MUAC, BMI, BVI	Counselling and advice +/- referral	Attended first appointment at food supplementation services	MUAC/BMI/BVI
Overweight	MUAC, BMI, BVI	Counselling and advice		MUAC/BMI/BVI
Anaemia	Hemocue	Iron and folic-acid supplementation (3 months supply) if anaemic. If severely anaemic (<8g/dl) refer to health facility.	Attended first appointment at health facility.	Anaemia

Poor oral health	Questions on oral health.  Visual inspection.	Advice, gift of toothpaste and toothbrush, fluoride varnish application +/- SDF application +/- referral	Attended first appointment at dentist	Reported pain or swelling. Frequency of tooth brushing
Uncircumcised	Question on circumcision status. Visual inspection.	Referral for VMMC (males only)	Attended first VMMC referral appointment.	Circumcised
Unprotected sex	Question (s) on sexual activity	Risk reduction counselling, Provision of condoms, Provision of modern contraceptives (emergency contraception, depot injections, oral contraceptive pill) (females only)  PrEP (females only)		Frequency of unprotected sex  Modern contraceptive use (females)  PrEP use (females)

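### Appendix 1 counts every uncircumcised hub male as positive for the primary outcome, but section 3.7.2 refers only those who ask for VMMC, so males who do not ask can never count as managed

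*Protocol*

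**What the plan says.** Three places in the protocol bear on this point.

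- **Section 3.7.2, VMMC (hubs only).** Status is asked of hub attenders: "During the background assessment males accessing services in the community will be asked if they are circumcised". Referral then depends on two things, status and a request: "If they are not circumcised and request VMMC then expedited referral will be arranged".
- **Appendix 1, row for uncircumcised males.** The screening-tool column reads "Question on circumcision status. Visual inspection", with no mention of a request. The two management columns stand under the header "Primary Outcome: Appropriate on the spot care or complete appropriate referral". For this row the on-the-spot column holds only "Referral for VMMC (males only" and the referral column holds "Attended first VMMC referral appointment". There is no entry for counselling, or for a service that was offered and not wanted.
- **Section 6.1.** "Completed referral is defined as attending at least the first referral appointment". A participant with several conditions must have completed care or referral for each of them to enter the numerator.

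Section 6.3 reports the primary outcome as one proportion with a 95% confidence interval for each of four age-by-sex groups. Section 6.2 plans on 500 per group, 30% screening positive and 75% of those correctly managed.

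**The concern.** VMMC is voluntary, and section 3.7.2 treats it that way. Appendix 1 treats the same status as a problem that needs a referral. Taken together with the all-conditions rule, a male who exercises the choice that section 3.7.2 gives him becomes a failure of the programme. Treating his anaemia or completing his eye referral would not change that.

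This affects the primary outcome in the older male group. Its denominator grows with people who have no route to success, so the reported proportion falls for a reason unrelated to whether identified problems were managed. The planning rates in section 6.2 make no visible allowance for it.

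**Working it through.** **Step 1: reading the rules together.** Take a hub male who is uncircumcised and does not request VMMC.

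| Question | Source | Answer |
|---|---|---|
| Is he screen-positive? | Appendix 1, screening by status | Yes |
| Is a referral arranged? | Section 3.7.2, on request | No |
| Does the on-the-spot column offer another success? | Appendix 1 | No, its only entry is a referral |
| Can he have attended a referral appointment? | Appendix 1, section 6.1 | No, none was arranged |
| Can other well-managed conditions compensate? | Section 6.1 | No, each condition must be completed |

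The header joins the two columns by *or*, so an issued referral might count as on-the-spot care. His chance of success is zero on that reading too, because no referral is issued.

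**Step 2: the plan's own figures.** Section 6.2 takes 150 of 500 positive (30%) and 75% managed (0.75 × 150 = 112.5; the protocol writes 112). The interval stated there, ±1.7%, does not reproduce: 1.96 × √(0.75 × 0.25 / 150) = 0.069, or ±6.9 points. That is a separate matter and nothing below depends on it.

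**Step 3: illustration of size.** The protocol gives none of these three inputs, so all are assumptions:
- h, hub share of males aged 15–19: 0.25 to 0.50
- u, share of hub males uncircumcised: 0.5 to 0.9
- d, share of those not requesting VMMC: 0.3 to 0.9

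A further assumption is that 30% are positive for something else, independently of circumcision status. The value is borrowed from section 6.2.

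Share of the stratum that is positive: P = (1 − h) × 0.3 + h × [u + (1 − u) × 0.3].
Forced failures: F = h × u × d.
Highest attainable primary outcome: 1 − F/P.

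| h | u | d | P | F | Highest attainable |
|---|---|---|---|---|---|
| 0.25 | 0.5 | 0.3 | 0.225 + 0.1625 = 0.3875 | 0.0375 | 90% |
| 0.25 | 0.7 | 0.7 | 0.225 + 0.1975 = 0.4225 | 0.1225 | 71% |
| 0.50 | 0.7 | 0.7 | 0.150 + 0.3950 = 0.5450 | 0.2450 | 55% |
| 0.50 | 0.9 | 0.9 | 0.150 + 0.4650 = 0.6150 | 0.4050 | 34% |

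These are ceilings: they suppose that every other positive participant is managed. If the others were managed at the planned 75%, the result would be 0.75 × 0.90 = 68% at the mild end and 0.75 × 0.34 = 26% at the severe end.

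**Step 4: effect of the scoring rule alone.** Take h = 0.5, u = 0.6 and 30% requesting. Assume that 75% of requesters attend and that other conditions are positive in 30% and managed in 75%, all independent.
- As written: 500 × [0.15 + 0.5 × (0.6 + 0.4 × 0.3)] = 255 positive, and the primary outcome is 43%.
- Counting only requesters as positive on this item: about 182 positive, and the outcome is 74%.

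With 10% requesting, the two figures are 35% and 75%. With 50% requesting, they are 51% and 73%. Management of conditions is the same in each pair; only the scoring differs.

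**The case against.** The strongest reply is that automatic failure is a deduction. No sentence says how a male who does not want VMMC is scored. The outcome speaks of appropriate care and appropriate referral, and section 3.7.2 could be read as saying when a VMMC referral is appropriate. Section 3.7.2 calls its own content and Appendix 1 drafts, section 3.1 leaves the target conditions to be finalised late in Phase 1, and a statistical analysis plan may settle the scoring. This limits how firmly one can say what the analysts will do. It does not remove the conflict: the text as it stands yields a definite score for these males, and nothing in it softens that score.

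Several stronger readings are tempting and are not supported.

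- *Attendance at VMMC is required.* The *or* in the Appendix 1 header leaves room to count an issued referral, so males who do request are not necessarily affected.
- *The older male result would mostly reflect VMMC preference.* That depends on inputs the protocol does not give. At the mild end above, forced failures are 0.0375 / 0.3875 = about 10% of positives.
- *The ceiling is 13–77%.* This is the same formula for hub males alone (h = 1). The 75% planning rate is for a whole age-by-sex group, which also includes school males, so the two should not be compared.
- *Comparisons between groups are invalid, or a school/hub split is needed.* Section 6.3 presents the four groups separately with no test between them. HIV and STI testing are also hub-only by design, and section 6.1 already reports each condition individually. A split is a preference.
- *Schistosomiasis has no success criterion.* It is screened for ("We will therefore test initially only for S. haematobium using a urine filtration lab test"), and no row for it appears in the Appendix 1 text at hand. That text was extracted from a PDF and a row may have been lost. Section 3.7.2 also promises treatment to those who test positive, which fits the general definition of on-the-spot care.

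**Conclusion.** The contradiction holds. As written, an uncircumcised hub male who does not request VMMC is counted in the primary-outcome denominator and cannot reach the numerator, on either reading of the Appendix 1 columns. The direction is certain: downward, in the older male group. The restriction to hubs comes from section 3.7.2; the Appendix 1 row itself says only males.

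The size cannot be found from the protocol. Under the assumptions stated (hub share 25–50%, uncircumcised 50–90%, not requesting 30–90%, 30% positive for something else), the best result the stratum could show is about 34–90%, against the planned 75%. The effect could be modest or could dominate the result. The flaw lies in how the outcome is scored, and it can be put right before analysis.

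**What to change.** Reconcile section 3.7.2 (VMMC), section 6.1 and the Appendix 1 row on two points: who counts as screen-positive for this item, and how a declined offer is scored in the primary outcome. The aim is that not requesting a voluntary service is not recorded as failed management. Either of these would do it:

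- score the item in the composite only where a VMMC referral was issued; or
- take it out of the composite and report VMMC uptake as a separate measure.

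The same edit should say whether an issued referral or attendance is what counts, and that the row applies to hubs only if that is intended. This changes outcome scoring only; it proposes no referral or clinical rule.

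The sponsor should also check that Appendix 1 has a row for schistosomiasis, since section 3.7.2 and Station 4 of section 3.7.3 screen for it.

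The cost is an edit to one Appendix 1 row and a sentence in section 6.1. No new data are needed provided that the request and the issue of a referral are recorded at the visit. Fewer older males would count as positive, so the interval for that group would rest on a smaller denominator: in the example with 30% requesting, about 182 in place of 255.
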